5.2.3 Other measurable changes

- Difference between the Clinical Frailty Indices
- Difference between the Technical Frailty Indices
- Difference between the Combined Frailty Indices

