On the other hand, the FrailSafe system attempts to depict a subject's frailty status in a more sophisticated and precise way. It consists of various sensors with the ability to record a large amount of data corresponding to several parameters like weight, body fat, blood pressure, pulse waves velocity, heart and respiratory rate, physical strength and activity, postural and movement information, localisation and cognitive performance. Most of the parameters' measurements will take place in real time circumstances in the person's natural environment, in the least invasive way possible. One of the originalities of the project is that the FrailSafe system will be developed and ameliorated during the study's evolution with the help of the preliminary results that will return to the engineers the participant's feedback and experience.

Using this large-scale data collection methodology, it will be possible to make comparisons between the clinical expression of different frailty levels and also between the performance of various measurements and tools to identify and even predict frailty.

Outcomes to be evaluated will be some hard and proxy clinically significant events, the evolution of frailty status of each individual (as measured by structured frailty indices) and the ability of each instrument to measure accurately frailty and its modifications and to predict frailty related outcomes. A secondary outcome (during the phase of parallel Evaluation and Control groups' testing) will be also to evaluate the possible difference in terms of evolution of frailty status between the individuals who received the FrailSafe system feedback and guidance and those who did not. Compliance rates and user satisfaction will be also tested. Shorter periods of monitoring will be compared with longer periods of monitoring to identify cost effective approaches.

By emerging the parameters and instruments the most efficient to detect, quantify and predict frailty, this project aims at constructing new and novel evaluation tools which will serve as frailty biomarkers of high accuracy and predictive value. The translation of these results in clinical practise could contribute to the organisation of strategies to prevent frailty and loss of autonomy both in individual and in population scale.

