2.2 Participants' characteristics

The Clinical study will be performed in 3 Clinical Centers: University of Patras (UoP), Greece; INSERM-Nancy, France; and MATERIA- Nicosia, Cyprus. Each Center will recruit 170 individuals for the FrailSafe study. By this way a total of 510 community living subjects aged 70 years and older will be recruited. The inclusion and non-inclusion criteria are demonstrated in table 1.

Table 1. Inclusion and exclusion criteria

Inclusion criteria
Age ≥70 years
Informed consent provided
Exclusion criteria
Lack of wish to participate
Consent withheld
Inability to give consent because of incapacity
Inability to walk
Inability to speak Greek or French (see clinical centers)
Diagnosis of clinically significant cognitive impairment or score less than 24 on the Mini– Mental State Examination
Diagnosis of advanced malignancy, other terminal illness or an estimated life expectancy of less than 12 months
Active psychiatric disorder based on medical records or clinical opinion at the time of recruitment, current substance users, or excessive alcohol drinkers.

The numerical threshold for "older age" has always been controversial, though most widely accepted was the age of 65 years, corresponding in the usual age of retirement. Still, nowadays "young old" individuals maintain a good general health condition and with the exception of special cases, frailty is most likely to be encountered in older age ranges. In the FrailSafe study, since we need to include people in non-frail, pre-frail, as well as frail conditions, it was decided that the age threshold will be that of 70 years.

In order to be able to comply better with the requirements of the study (usage of technical material, cooperation for the testing of novel equipment, need for participant's feedback and relatively long follow up period), subjects with highly debilitating conditions, such as inability to walk, presence of clinically significant cognitive impairment, or active psychiatric

disorder will be excluded from the study. Similarly, subjects with serious medical conditions that convey a guarded prognosis (estimated life expectancy of less than 12 months) will be excluded as well.

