2.3 Groups

All participants will be given a unique number by the time they are allocated in four groups (table 2), with the addition of the code number of each centre in front: (1 for Patras, 2 for Cyprus and 3 for Nancy). For each centre, participants with numbers 001 to 080 will belong to the Start Up Group (A), the 40 following will belong to the Main Group (B), the 25 following afterwards will belong to the Evaluation Group (C) and the last 25 to the Control Group (D). The Evaluation Group (C) will be further divided in two parts: participants with numbers 121-140 will belong to the "standard" Evaluation Group; while those with numbers 141-145 will belong to the Long Term Evaluation Group, with an augmented intensity of following up.

Group	Serial Number
A- Start Up	001-080
B- Main	081-120
C- Evaluation	121-145
Ci- Standard Evaluation	121-140
Cii- Long term Evaluation	141-145
D- Control	146-170
With the prefix of the centre number	1 for Patras, Greece
	2 for Nicosia, Cyprus
	3 for Nancy, France

Table 2. Participants' ID numbers

In case of exclusion or premature withdrawal of a participant, (s)he has been replaced by a new subject, to whom a new unique ID number has been given. The substitute subjects were given the number of the individual they have replaced with the addition of 500. For example, if the participant number 1094 withdrew from the study (subject number 94 from the first recruitment centre), the subject that replaced him/her will take the number 1594

(=1094+500). For subject number 3164 who withdrew (participant number 164 from the third recruitment centre), the subject replacing him/her will take the number 3664 (=3164+500). However, participants' replacements took place only until M19. Any subject that dropped off after July 2017, has not been and will not be replaced due to lack of time for catching up with the minimum follow up time period required (M19 represents the middle timeline of the project).

The number of the participants allocated in each group is already agreed in the original proposal and corresponds mostly to issues of availability of material and workforce in the context of actual financial potential and less to pure mathematical calculations, due to the originality of the project and the absence of a previous reference to consider for sample size calculations.

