- Non-frail and mostly pre-frail individuals are more likely to benefit from interventions in terms of prevention of evolution of their frailty status (MO3), than the already frail ones that are less likely to regress to a previous frailty status.
- Especially the pre-frail individuals, that outweigh other categories in our population, are those who are traditionally considered to benefit more from potential interventions and thus are generally the target of the standard CGA (ie, excluding patients who are either too well or are too sick to derive benefit) (MO4) (1). If the

FrailSafe system is to be tested for its added value on the standard CGA (main medical objective), pre-frail individuals should be the dominant target group.

- Our study focuses on prevention (MO6), therefore, a smaller number of already frail people should be allowed. However, they should also exist in our study population in order to enable us to make comparisons and draw conclusions.
- From the very first analysis that has been performed and presented in D2.6 Behavioral management, we observe that the pre-frail category almost constantly scores in between the performances of the non-frail and the frail group in all tests and parameters. This emphasizes the fact that they constitute a dynamic intermediate category with the potential to approach either the one or the other extreme (MO5). Thus, the results of potential interventions could be measurable and could contribute to the prevention of category shifting towards frailty.
- Under the prism of a potential exploitation of the FrailSafe end product in the future, individuals, health care professionals, insurance companies and health policy makers could be more interested to apply the integrated FrailSafe system in people that are already threatened by a devastating health condition such as frailty (ie the pre-frails), rather than devoting resources in a totally healthy population, who might not be eligible for reimbursable health interventions. Therefore this frailty category is considered to be of great interest for the FrailSafe project (MO7).

The above listed proportions are calculated on the total of participants, in the sum from all three centers, so different percentages may be present within groups from Cyprus, Greece and France. However, the same criteria (Fried's)(2) (table 9) will be applied in all clinical centers.

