This stratification of frailty according to Fried's criteria will not be used in the analysis of data. The study population will be considered as a whole, from which new frailty metrics will be identified using both hard and proxy outcomes; the latter will be based on the change of clinical and FrailSafe parameters.

The sample in this study should ideally be randomly selected from the general population in those aged \geq 70 years. This would require a larger number of participants and a larger number of study workforce, as well as equipment, in order to include individuals with the right case mix of frailty levels and a representative number of comorbidities. Undoubtedly, such a design would have been preferred and would have provided strong and reliable clinical results. However, current financial resources in this Horizon 2020 call, which are split among technological development and clinical evaluation, were not sufficient for this type of methodology.

It is understandable that transition among the groups as defined by Fried's criteria might not be easily observed with the current study design, as number of participants, time span and number of simultaneous FrailSafe assessments are limited. On the other hand, functional changes or proxy outcomes expressing loss of functional reserve is likely to be detected when the study group is examined as a whole. The choice of the current clinical study methodology was a compromise between an ideal approach and a more practical solution, though hampered by numerous limitations.

In addition, in each of the three frailty status, at least 7 have prior stroke, 7 MCI (Mild Cognitive Impairment), 7 either osteoporosis for women or osteoarthritis for men and 7 nothing of the mentioned above. There is no particular concern in which group they will

belong. If this will not be achieved by randomization, the investigator, who will be in charge to overall monitor randomization, will intervene to further randomly stratify cases to obtain this pre-specified study objective.

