Randomization will take place for groups C (Evaluation) and D (Control)(section 2.4) in a later study period (M10-M30). The randomization has proven to be practically difficult for groups A (Start Up) and B (Main), due to the almost coincidence of their recruitment in the beginning of the study and the large number of participants they required. As the dissemination campaign advanced progressively, it turned out to be difficult to have in our availability, since the very initial phase of the clinical study, an even larger pool of participants in order to strictly randomise them. Instead, we included in the first group the first 80 subjects that expressed their interest for participation in each centre, followed by the 40 consequent ones, who were finally allocated to group B. We estimate that since in the present phase of the clinical study the objective is to validate the FrailSafe system and to test its detection sensitivity and not to compare interventions (as will be during the groups C and D parallel evaluations), and since we have no reason to believe that the subjects who were recruited during the first dissemination activities differ significantly from those who were informed about the study in a later stage of the recruitment campaign, the consortium believes that this lack of randomization in the very first phase of the study will not affect results, since comparison between groups will take place later between group C (evaluation) and D (control).

In a later period during the study (M20-M30), recruitment campaigns will start again in order to create the pool of eligible subjects from which participants for group C and D will be randomly selected.

In addition, the participants of the evaluation group C will be further randomized (1:1) into two categories either to receive a tailored set of lifestyle, nutrition and exercise recommendations (predetermined recommendation and "intervention" proposals based on the monitoring performed using the Frailsafe system) or to receive general life style recommendations (standard care). The technical personnel responsible for the extraction and analysis of data will be blind on randomization procedure.

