where a, b and c positive parameters that indicate the starting point and the rate of linear and more rapid (quadratic) change, respectively. Zero values of b and c model the steady state. If less than three time points are available, the estimation of c is not possible and thus will be taken as zero. After completing three clinical evaluations, c can be also estimated.

The second step in the methodology will be to identify the important FS variables as the ones which correlate well with any of the estimated proxy variables f_i . Since an event can have a delayed effect, lag correlations will be also examined to identify possible latencies. If such correlations prove to exist, we will have the means to predict future responses using the FS devices.

Furthermore, in the last step of our methodology when more data become available, statistical (survival) analysis will be performed, using for example the Cox proportional hazards model, in order to find frailty indexes that predict the hard outcomes. This step will have more statistical power when a adequate number of hard outcomes will have happened, thus it will be applied after the 2nd clinical evaluation of group A, as well as by the end of the project. More details on the proposed scores (technical and medical) are provided in Section 5.1 and Appendices I and II.

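### Section 2.4 bars the Fried category from the analysis with no exception for C versus D, and the C-versus-D measures are framed only as change, with no use of the M31 value stated

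*Protocol*

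**What the plan says.** Section 2.1 makes C versus D a secondary outcome: "to evaluate the possible difference in terms of evolution of frailty status between the individuals who received the FrailSafe system feedback and guidance", set against people without them. Section 2.4 plans randomisation for these two groups.

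The measures that could express evolution are all written as change. Section 5.2.3 lists "Difference between the Clinical Frailty Indices", and likewise for the Technical and Combined indices. Section 5.2.2 says changes in the proxy outcomes will be assessed at intervals and between entry and end of study. Neither section names a test, model or covariate for C versus D.

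Section 2.4 says: "This stratification of frailty according to Fried's criteria will not be used in the analysis of data". The sentence after it explains that the study population is taken as a whole so that new frailty metrics can be found.

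Groups C and D have clinical evaluations at M31 and M36 (Sections 2.5, 4.4.1, 4.4.2, 4.5). Fried's criteria are recorded at entry in every group (Section 4.1, step 4).

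**The concern.** The exclusion in Section 2.4 is a positive statement, not a silence. Read literally, an analysis plan that follows the protocol may not use the Fried category in C versus D, although it is a baseline variable planned for everyone in that comparison. The stated reason gives no ground for this. Finding new metrics in the whole population is a different task from estimating a difference between two randomised arms. Section 2.4 also lets the investigator intervene in the randomisation to fill comorbidity quotas within each frailty status, so frailty status may bear on allocation and still be kept out of the analysis.

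Framing evolution as change adds to this. With one baseline and one follow-up value, an unadjusted change score is less precise than the follow-up value adjusted for baseline whenever the two variances are equal and the correlation is below 1. It also carries part of any chance baseline difference into the estimated effect. Section 2.3 says group sizes follow material and workforce rather than a calculation, and Section 5.4.2 says the number of participants cannot be changed. Precision for C versus D therefore has to come from the analysis.

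**Working it through.** **Headcount.** "The Clinical study will be performed in 3 Clinical Centers" (Section 2.2). Section 2.3 gives 80 + 40 + 25 + 25 = 170 per centre, and 3 × 170 = 510, as stated. Groups C and D have 3 × 25 = 75 each, 150 in all. The protocol has no power calculation to reproduce.

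**Availability at M31.** Sections 4.1 and 4.5 together give group D Tables 4 to 14 at entry or M31, and Tables 5 to 14 at M36. That covers all proxy outcomes: gait speed, MoCA/MMSE, GDS, weight and self-rated health. Group D has no FrailSafe sessions (Section 2.5), so it has no Technical or Combined index. It has no housing evaluation (Section 3.4), so its Clinical Frailty Index lacks the housing items. In group C the housing evaluation is made only at the first home visit.

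**Assumptions (not in the protocol).** Two-sided alpha 0.05, no dropout, equal variance (SD 1) at M31 and M36, C treated as one arm, correlation ρ between M31 and M36 from 0.5 to 0.9.

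**Formulas.**
- Residual variance: unadjusted change 2(1−ρ); M36 adjusted for M31 1−ρ².
- Ratio of adjusted to change: (1−ρ²) / [2(1−ρ)] = (1+ρ)/2.
- Detectable difference at 80% power: (1.960 + 0.842) × SD × √(2/75).
- Number per arm on change that would match 75 adjusted: 75 × 2/(1+ρ).
- Shift of the change-score estimate for an M31 imbalance of one standard error: (ρ−1) × √(2/75) = (ρ−1) × 0.163 SD.

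**Worked case, ρ = 0.5.** Detectable on change: 2.802 × 1.00 × 0.1633 = 0.457 SD. Adjusted standard error: √0.75 × 0.1633 = 0.1414. Then 0.457/0.1414 − 1.960 = 1.275 (before rounding), which gives power 0.899.

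| ρ | Variance, change | Variance, adjusted | Ratio | Detectable, change → adjusted (SD) | Adjusted power where change has 80% | Matching n per arm on change | Shift for 1 SE imbalance (SD) |
|---|---|---|---|---|---|---|---|
| 0.5 | 1.00 | 0.75 | 0.75 | 0.457 → 0.396 | 90% | 100 | −0.082 |
| 0.7 | 0.60 | 0.51 | 0.85 | 0.354 → 0.327 | 86% | 88 | −0.049 |
| 0.8 | 0.40 | 0.36 | 0.90 | 0.289 → 0.274 | 84% | 83 | −0.033 |
| 0.9 | 0.20 | 0.19 | 0.95 | 0.205 → 0.199 | 82% | 79 | −0.016 |

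**Check by simulation.** In 4,000 trials of 75 versus 75 with no effect, the variance ratios were 0.73, 0.87 and 0.97 at ρ = 0.5, 0.7 and 0.9. Both estimators averaged zero to within 0.002 SD.

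**Degrees of freedom.** M31 value 1, centre 2, Fried category 2: 5 in all. The residual falls from 148 to 143. Any gain from centre and Fried category is not counted in the table.

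**The case against.** The strongest reply is that Section 5.2.3 defines quantities, not an analysis. A difference can be modelled with the M31 value as a covariate, and the arm coefficient is then the same as for the M36 value so adjusted. Covariates are commonly left to the analysis plan, and Section 2.4 itself foresees comorbidities as confounding factors. This stands. A reader might infer that C versus D is built on unadjusted change, but the protocol does not say so.

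The second reply is that the Fried sentence closes a discussion of the frailty mix set for groups A and B, and that Section 3.6.1 plans an autonomic sub-study by Fried class, so no blanket bar was meant. That may be the intention. The sentence still states no exception, and the sub-study shows that its scope needs to be written down.

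Other stronger readings also fail:
- Section 5.2.2 says "If less than three time points are available, the estimation of c is not possible and thus will be taken as zero", which for C and D leaves a two-point slope. That model serves to find FrailSafe variables that predict the proxies. Group D has no FrailSafe data, so it is not a C-versus-D analysis.
- Section 2.4 does not call the Fried category prognostic. It says who is more likely to benefit, which is effect modification. Its remark on centres, "so different percentages may be present within groups from Cyprus, Greece and France", concerns proportions set for A and B.
- C versus D is not the only randomised comparison. Section 2.4 also randomises within group C, 1:1, between tailored and general recommendations, so C is not a uniform arm.
- Change scores under randomisation are not systematically biased. The shifts in the table are conditional on a chance imbalance.

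The Clinical Frailty Index already contains the Fried-type items (Table 22), so the Fried category adds less beside a baseline index than beside a single proxy.

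**Conclusion.** The point holds in a limited form. The defect in the text is the unqualified exclusion of the Fried category in Section 2.4, whose reason covers index derivation only. The change-only framing, with no stated use of the M31 value, is a weakness to settle at the same time rather than a stated error.

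If change were analysed unadjusted, the loss would be about 10 power points from an 80% start at ρ = 0.5, 6 at 0.7, 4 at 0.8 and 2 at 0.9. Over five months a stable measure could well lie at the high end, where the gain is small. The figures rest on the assumptions listed with the calculation. The comparison is secondary and its validity is not in question. The correction is still worth making, because it buys precision at almost no cost in a sample that cannot grow.

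**What to change.** (a) In Section 2.4, limit the exclusion: the Fried category is not used to derive the new frailty metrics, but may be a covariate in C versus D.

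(b) In Sections 5.2.2 and 5.2.3, or in the analysis plan, state that for C versus D each proxy outcome, and a Clinical Frailty Index restricted to items collected in both arms (so without the housing items), is analysed at M36 by a linear model. The model contains arm, the M31 value of the same measure, centre and baseline Fried category, and the arm coefficient is the effect. For weight loss, this means weight at M36 adjusted for weight at M31. The Technical and Combined indices stay out of this comparison.

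The cost is a few sentences and 5 covariate degrees of freedom out of 148. No new data are needed.

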APPENDIX I- Clinical Frailty Index (CIFI)

We define loss of physiological reserve changes in ten domains investigated by the clinical evaluation assessment (health status, physical performance, nutritional, cognitive, psychological, wellness etc). We add up scores from all variables in order to have an initial rough index that expresses frailty parameters altogether. Due to lack of sufficient data in the literature about the specific weight of each item and even of each domain, we have chosen to initially take equal weights for each item, aiming at validating our model in the end of the study in terms of frailty evolution predictive value, as expressed by outcomes occurrence.

Items that will contribute to the generation of the CIFI are listed in table 22.

Table 22. Components of Clinical Frailty Index

Items	
Medical Domain (M)	Each polypathology /Comorbidities (M)
	Comorbidity's impact (M, P, s, c)
	Polymedication (M, p, c)
	Orthostatic hypotension (M, p)
	Visual impairment (M, S, p)
	Hearing impairment (m, S, c)
General Condition	Unintentional weight loss (M, ψ)
Domain (Μ, ψ)	Self-reported exhaustion (M, ψ)
Physical Condition	Balance (single foot standing) (P, m)
(P, m, c)	Gait-related task speed* (P, c)
	(Timed Get Up and Go test)
	Gait - speed 4 m (P, m)
	Lower limb strength (P, m)
	Grip strength –dynamometer (P, m)
	Qualitative evaluation of mobility (P, m)
	Low physical activity (P, M, s, ψ)
Nutrition (M, Ψ , c, s)	Too low BMI (Μ, Ψ, p, c, s)
	Too high BMI (M, Ψ, Ρ, ϲ, s)
	Waist circumference (M, Ψ , P, c, s)
	Lean body mass (M, P, ψ)
	Total MNA score (M, Ψ, p, c, s)
Cognitive Domain	MMSE scores (C, ψ , m)
(C, ψ, m, s)	MoCA score(C, ψ, m)
	Subjective memory complaint(C, ψ , m, s)
	Natural language analysis (C, Ψ)
Psychological Domain	GDS-15*(Ψ, S, c)
(Ψ, S, c)	Self-rated anxiety (Ψ, S, c)
	Natural language analysis (C, Ψ)
Social Domain (S, Ψ , m)	Living conditions (S, Ψ , p, m)

Social Domain (S, Ψ, m)	Leisure activities (S, Ψ , p, m)			
	Membership of a club (S, Ψ , p, m)			
	Number of visits and social interactions per week (S, Ψ , p, m)			
	Number of telephone calls exchanged per week (S, ψ , m)			
	Approximate time spent on phone per week (S, ψ , m)			
	Approximate time spent on videoconference per week (S, ψ)			
	Number of written messages sent by the participant per week (S, ψ , m, p)			
Environmental Domain	Subjective suitability of the housing environment according to			
(S, P, m)	participant's evaluation (S, P, m)			
	Subjective suitability of the housing environment according to			
	investigator's evaluation (S, P, m)			
	Number of steps to access house (S, P, m)			
Wellness (Ψ, S, M, P, c)	Quality of life self-rating (Ψ, S, M, P, c)			
	Self-rated health status (M, Ψ)			
	Self-assessed change since last year (M, ψ)			
	Self-rated anxiety (Ψ, S, M, P, c)			
	Self-rated pain (M, P, ψ)			
Lifestyle (Ρ, Μ, ψ,s)	Smoking (Μ, Ψ, p, s)			
	Alcohol (Μ, Ψ, S)			
	Physical Activity (P, M, ψ,s)			
Tags (reflecting impact of	of each item on CIFI)			
Physical: P dominant, p recessive				
Medical: M dominant, m recessive				
Social: S dominant, s recessive				
Cognitive: C dominant, c recessive				
Psychological: Ψ dominant, ψ recessive				

